4.8. Subject Follow-Up

After completing CR or a subject’s last CR visit, follow-up visits 1 and 2 will be scheduled, the former scheduled within 10 days of last CR visit and the latter scheduled at 6 months \pm 15 days after last CR visit. Data collected at follow-up visit one will be nearly the same as that gathered during baseline. This includes both QOL instruments (Dartmouth COOP, EQOL), a CPX test, the 6MW, PHQ-9, Rate your Plate, and 5x sit-to-stand. Data collected at follow-up visit two includes both QOL instruments (Dartmouth COOP, EQOL), a CPX test, the 6MW, PHQ-9, Rate your Plate, and frailty assessment.

Table 4. Schedule of Trial Events and Time line

Patient Care Event	Screening and Baseline	Weeks 1-26 or CR visits 1-36*	F/up visit 1 within 10 d after last CR visit	2 mo after last CR visit	4 mo after last CR visit	F/up visit 2 at 6 mo after last CR visit
Testing						
CPX	X		X			X
6MW	X		X			X
Dartmouth COOP	X		X			X
EuroQOL-5D	X		X			X
Rate your plate	X		X			X
Mini-cog	X					
5x sit-to-stand	X		X			X
iPAQ	X		X	X	X	X
PAST	X		X	X	X	X
Training						
Exercise sessions		X				
Telephone calls				X	X	

*Patients will have 6 mo to complete 36 visits; iPAQ=International Physical Activity Questionnaire; PAST = Past-day Adult Sedentary Time Questionnaire

5. Trial Endpoints

5.1. Primary endpoint

R61 Phase. In conjunction with study investigators, stakeholders, and NHLBI staff, prepare and operationalize a clinical trial that evaluates the effect of a HYCR program on attendance to CR. This includes finalizing the protocol, obtaining any institutional review board approved amendments, developing the manual of operations, establishing data safety monitoring board, hiring and training CR and research staff, and demonstrating the ability to screen and enroll patients into the trial.

R33 Phase. The number of CR sessions completed within 6 months

5.2. Secondary Endpoints.

R33 Phase only.

1. Percentage of patients completing 36 CR sessions within 6 months
2. Change in exercise capacity upon completion of CR
 - a. Peak VO₂
 - b. Six minute walk distance
3. Change in quality of life upon completion of CR
4. Exploratory endpoints
 - a. Change in exercise capacity at 6 mo after completion of CR
 - i). Peak VO₂
 - ii). Six minute walk distance
 - b. Change in quality of life at 6 mo after completion of CR
 - c. Change in sedentary behavior and physical activity habits (home, work, recreation), the latter of which does not include exercise in CR
 - d. Economics and resource utilization associated with of CR.

Home- or hybrid approach to CR (with or without telemedicine) is often viewed as a “negative” financial business model due to lack of revenue (and increased patient care expenses and staff time). The cost effectiveness, economics and resource utilization of the HYCR program will be determined and compared to the similar data for CBCR. In both CR models we will collect and calculate costs associated with program implementation (staff time, HR monitors, and upgrading desk tops for telemedicine) as gathered from both administrative data within the CR unit and from the Health System’s Corporate Accounting/Financial Services Department. We will also collect costs from participants at follow-testing, including direct nonmedical and medical costs (including value of time of the participants attending a program, waiting, and travel). In a subset of

our his project's full cohort, for patients insured Health Alliance Plan or Blue Cross and Blue Shield of Michigan, we will identify and compare reimbursement and health care utilization during CR and for the 6 month period of time after CR is completed

6. Safety

Consistent with what is known today about the practice of cardiac rehabilitation, the level of incremental risk for major unexpected adverse events (death, events requiring hospitalization) that are probably related to a subject's participation in this project is anticipated to be extremely low.

6.1. Safety assessment.

Safety assessments will consist of the recording and monitoring of all safety related events. Results from patient assessments (e.g., CPX results, ECG rhythm strips [if any]) that include safety parameters performed as part of the patient evaluation or trial protocol will be maintained in the patient's research chart and considered to be source documents.

6.1.1. Adverse and Serious Adverse Events or Experience

An adverse event (AE) is defined as any untoward medical occurrence (new onset or change in disease state) in a patient that is unfavorable and unintended (e.g., new onset chest pain, near syncope, new onset atrial fibrillation), regardless of whether or not it is considered to be related to the intervention. A serious adverse event (SAE) is defined as any untoward medical occurrence that results in any of the following: death; persistent or significant disability/incapacity; hospitalization; stroke; fall requiring medical attention; is life threatening; or requires or is considered serious such that the patient may require medical or surgical intervention to prevent any of the previously listed events.

For the purposes of iATTEND, the project will follow all policies and procedures set forth by Henry Ford Hospital, its Office of Research Administration, and its Institutional Review Board (IRB). SAEs and AEs of interest will be collected after randomization and through follow-up visit 2 and recorded on a CRF. The project management team (PMT) will forward this safety data to the DSMB on a regular basis (e.g., quarterly), which will perform routine evaluations of such.

Additionally, although likely very rare, unexpected SAEs that are possibly attributable to rehabilitation, as determined by the trial PI (e.g., occurring during or within 3 hours after exercising), will be reported to the IRB and DSMB within 10 days of occurrence.

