6.1.2. Assessment of Actionable Events Immediately Proximal to CR

A secondary analysis is planned of actionable events (both AE and SAE) sustained immediately prior to, during, or immediately after (during recovery) an exercise training session. These represent both major events that may require hospitalization (e.g., myocardial infarction, fall) or an emergency room visit, as well as events that often occur in CR and may lead to with-

holding a patient from starting exercise, stopping a patient from continuing to exercise, or requiring notification of the patient’s a physician (e.g., symptomatic hypoglycemia requiring oral glucose supplementation, new onset or worsening angina/ischemia, falls, persistent hypotension).

7. Study Organization

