The Data Safety Monitoring Board (DSMB). For this trial the DSMB will be an "internal DSMB", comprised of 4 individuals that are independent of the NHLBI, trial investigators, and trial management. The NHLBI will approve the membership of the DSMB and the DSMB is advisory to the NHLBI and the trial's Steering Committee.

The primary endpoint for this study is number of sessions attended (not a clinical outcome such as mortality). However, trial safety is always a concern. Therefore, rare, untoward, unexpected major events related to exercise training or exercise testing (i.e., during or within three hours) may occur and will be monitored, such as death or events requiring hospitalization (e.g., myocardial infarction, syncope, arrhythmia, fall). These events will be reported to both the IRB and DSMB per existing institutional and protocol requirements (i.e., within 10 days) and documented in the subject's study file.

Monitoring of events. A DSMB meeting will be held in-person (with teleconference capabilities) every six months, during which a comparison will be made of any excess, untoward events. If needed, the DSMB will advise the NHLBI and Steering Committee accordingly. Minor events, such as falls not requiring emergency care, angina, and ST segment changes during testing that are suggestive of myocardial ischemia will be documented in the subject's study file.

Relative to suspending or discontinuing a specific subject's participation in CR and/or the trial assessments due to a clinical indication (worsening symptoms, compromising arrhythmia), [name] will consult with co-investigators Drs. [name] or [name] to ensure that all applicable and relevant Henry Ford Hospital and Preventive Cardiology Unit program- and patient-level clinical policies and procedures are followed. With the subject's permission, and to assist with their care, their own physician will be contacted regarding the relevant clinical findings. The Steering Committee will be informed of the above.

Since a clinical endpoint such as death or re-hospitalization does not represent a trial endpoint or outcome measure for this project, the DSMB will not have to address the issue of trial continuation relative to endpoint futility. All subjects will be evaluated for the specified duration of the trial for all primary and secondary outcomes measures. The number of subjects that withdraw consent from trial participation will be tracked and reported.

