The monitoring for unexpected major adverse events and minor events, as well as patient withdrawals, will occur continuously through the study by the project manager and research coordinator. Major events will be discussed within the project management team.

It will be the responsibility of the study coordinator, in conjunction with [name], to ensure that unexpected serious/major adverse events that occur within 3 hours of exercise are collected, summarized and reported within 10 days to the local IRB and to the DSMB. Although the occurrence of an unexpected, major adverse events is not anticipated and felt to be extremely rare, any such events that do occur will be investigated and discussed jointly between the principal investigator and the DSMB or its chair. Any policy or procedural changes that arise from such discussion will be incorporated into a revised study protocol. Subjects that withdraw consent from trial participation will also be tracked by the study coordinator and reported to the DSMB.

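### A fall needing medical but not emergency care is an SAE in section 6.1.1 and a minor event in Appendix A, so its place in the SAE count and its 10-day report depend on which text staff follow

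*Combined protocol and SAP*

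**What the plan says.** Section 6.1.1 defines an SAE by a list that includes "hospitalization; stroke; fall requiring medical attention; is life threatening". SAEs and AEs of interest are recorded on a CRF from randomization through follow-up visit 2 and forwarded regularly to the DSMB. An unexpected SAE that the principal investigator judges possibly attributable to rehabilitation goes to the IRB and DSMB within 10 days. Occurrence in the exercise session or the three hours after it is given as an example. AEs of interest are not defined.

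Appendix A works with major and minor events. Major events tied to exercise training or testing are illustrated by "such as death or events requiring hospitalization (e.g., myocardial infarction, syncope, arrhythmia, fall", and they carry the 10-day report. On the lesser class it says: "Minor events, such as falls not requiring emergency care, angina, and ST segment changes during testing that are suggestive of myocardial ischemia will be documented". The only record named there is the study file. Its closing paragraph gives the reporting duty as covering "unexpected serious/major adverse events that occur within 3 hours of exercise are collected, summarized and reported within 10 days".

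Section 6.1.2 plans a secondary analysis of actionable events around exercise sessions, AEs and SAEs together. Falls are an example in its upper tier (hospitalization or an emergency room visit). They appear again in its lower tier, whose examples include "new onset or worsening angina/ischemia, falls, persistent hypotension".

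Section 7.3 words the 10-day trigger in two ways: once as unexpected SAEs associated with exercise, and later as SAEs that are both unexpected and major.

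**The concern.** The thresholds for a fall do not match. Section 6.1.1 sets the line at medical attention of any kind, while Appendix A keeps a fall in the minor class until emergency care is needed. Between the two lies the fall seen in a clinic or by the patient's own physician. Because Appendix A joins serious and major with a slash, its minor class reads as non-serious, which contradicts 6.1.1 for exactly these falls.

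This is a safety-reporting rule, and the plan itself treats falls as a specific hazard of exercise. Section 4.3.1.b excludes patients with a slow sit-to-stand test, and Appendix A item (c) requires a check of gait, balance and stability before a patient uses equipment alone. Staff who follow Appendix A as written could leave an event that the protocol defines as serious without its SAE form and its 10-day report.

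**Working it through.** No arithmetic applies. The documents give no fall rate or SAE rate, and no sample-size figure depends on the definitions. The check sets the texts side by side for four grades of fall.

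| Fall | Section 6.1.1 | Appendix A | Section 6.1.2, if around a session and actionable |
|---|---|---|---|
| No medical attention | Not an SAE by the fall criterion; at most an AE | Minor | Included |
| Medical attention, not emergency care | **SAE** | **Minor** | Included under either label |
| Emergency care, no admission | SAE | Outside the minor example, below the level that illustrates major | Included, upper tier |
| Admission to hospital | SAE | Major, if tied to exercise | Included, upper tier |

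The second row is a contradiction. The third is an ambiguity: Appendix A's major examples are only illustrative, so the text neither includes nor excludes such a fall. The first and last rows agree.

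Next, the 10-day report for a second-row fall that is unexpected and happens during exercise or within three hours after it:

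1. Section 6.1.1: required if the principal investigator judges it possibly attributable, because the fall is an SAE.
2. Section 7.3, opening paragraph: required if it is associated with exercise, because the fall is an SAE.
3. Section 7.3, later paragraph: depends on whether this SAE is also major, a term that section does not define.
4. Appendix A, minor-event sentence: only a study-file entry is named.
5. Appendix A, closing paragraph: not required if serious and major are one category, because the fall has been called minor.

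One event therefore meets different reporting duties, and no sentence gives any of these texts precedence.

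Last, the 6.1.2 analysis. Its scope is AEs plus SAEs, and falls are named in both tiers, so moving a fall from SAE to AE leaves the total unchanged. Two routes of dependence remain. The AE/SAE breakdown shifts with the label. The total could also fall short if a minor fall is never entered on a CRF, which is possible because 6.1.1 sends only SAEs and the undefined AEs of interest to that form.

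**The case against.** The strongest reply is that the conflict is narrow and the plan has other safeguards. Study-file entry is not said to be exclusive: Appendix A files major events there too ("i.e., within 10 days) and documented in the subject's study file"). Section 6.1 calls for all safety-related events to be recorded and monitored, Appendix A monitors minor events continuously, and section 7.3 opens all AE and SAE records to the DSMB on request. Appendix A also opens with a general commitment to report defined unexpected adverse events to the IRB and DSMB. The slash in serious/major could be read as serious *or* major, which would let 6.1.1 control.

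Much of this stands, and it rules out several stronger readings that a reader might infer:

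- *That clinic-treated falls drop out of the 6.1.2 analysis or never reach the DSMB.* The analysis pools AEs and SAEs. The DSMB's six-monthly comparison is described as covering any excess of untoward events, without restriction to major ones. The text nowhere says such falls are kept off the CRF.
- *That angina is caught in the same contradiction.* It is not on the 6.1.1 SAE list, and new chest pain is an AE example there, so calling angina minor is compatible with a non-serious AE.
- *That the trial would falsely show no SAE excess with hybrid delivery.* Either rule applies to both arms. Table 3 shows different staff contact times, but nothing shows that falls would be classified differently by arm, and section 5 lists no SAE comparison as an endpoint.
- *That a count of misclassified events can be given.* It would rest on an assumed fall rate with no basis in the documents.

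The reply does not remove the core conflict. The general commitment in Appendix A carries no deadline and does not say which events are defined. Access on request is not a report. A favorable reading of the slash still leaves the minor-event sentence as it stands.

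**Conclusion.** The contradiction holds for one class of event: a fall that needs medical attention but not emergency care. For that class, the SAE count and the 10-day IRB and DSMB report depend on which text staff follow. The effect on the 6.1.2 analysis is limited to its AE/SAE split, or to incomplete capture if minor falls are not transferred to a CRF.

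The conclusion assumes that serious and major in Appendix A's closing paragraph name one category, and that no institutional policy or manual of operations outside these documents settles precedence. The wording conflict is certain, but the number of events it touches is unknown. There is no effect on the primary endpoint, sample size, power or efficacy analyses. It should still be corrected, because it is a contradictory safety-reporting rule and not merely a missing detail.

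**What to change.** Reconcile sections 6.1.1, 6.1.2, 7.3 and Appendix A to one event classification and one reporting route:

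1. Most simply, have Appendix A refer to the 6.1.1 AE and SAE definitions in place of its own major and minor classes. Where the sponsor sets the line for a fall is for it to decide; the need is that it be set once.
2. Bring the word major into line in 6.1.2, both parts of 7.3 and Appendix A. Removing the appendix classes alone would leave the later 10-day trigger in 7.3 resting on an undefined term.
3. State the 10-day trigger in one form and repeat it identically.
4. Define AEs of interest to include the event types that 6.1.2 will analyse, and state that they are recorded on the CRF. This need cover only falls and other events that are actionable in the 6.1.2 sense.

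The cost is a wording amendment, with IRB approval under section 11 unless it counts as administrative. The downside is a few more CRF entries and possibly a slightly higher SAE count.

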6.1.2. Assessment of Actionable Events Immediately Proximal to CR

A secondary analysis is planned of actionable events (both AE and SAE) sustained immediately prior to, during, or immediately after (during recovery) an exercise training session. These represent both major events that may require hospitalization (e.g., myocardial infarction, fall) or an emergency room visit, as well as events that often occur in CR and may lead to with-

holding a patient from starting exercise, stopping a patient from continuing to exercise, or requiring notification of the patient’s a physician (e.g., symptomatic hypoglycemia requiring oral glucose supplementation, new onset or worsening angina/ischemia, falls, persistent hypotension).

7. Study Organization

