This group of iATTEND involves a hybrid design, with the frequency of CBCR visits and HYCR visits individualized and modified based on the subject’s personal preferences and their family, transportation and work constraints. Per study eligibility criteria, patients in HYCR will engage in at least one CBCR visit. For those with no preferences as to their number of TM visits, they will be scheduled to complete 12 of their 36 visits as HYCR-TM, with the remainder being home-based without TM (up to one time per week) and/or CBCR 1 or more per week. Immediately following CR visit 1 (which will be CBCR), patient in HYCR will have the video app loaded to their smart phone or tablet (or that of a “willing to assist” family member or friend). HYCR patients receive a chest strap/wrist heart rate device to document HR before, during, and/or after exercise during the TM session. After CBCR visit 1, if the patient opts to complete the remainder of the CR session as HYCR, they will be provided with a home blood pressure unit for the regular reporting of resting blood pressure prior to each HYCR visit. HYCR subjects will be encouraged to engage in purposeful exercise ad libitum on their own each week.

Since both Blue Cross and Blue Shield of Michigan and Health Alliance Plan already cover CBCR and HYCR, only the co-payments will be covered by the project’s budget. For patients randomized to HYCR that have an insurer that does not yet cover CR delivered using TM (e.g., Medicare), their CR visits will be covered by the project’s budget. For all patients randomized to CBCR, their co-payments will be covered by the project’s budget.

Program education for patients in HYCR will be delivered using the twenty-eight, 7-15 min audio PDF’s that are free to access from the Health System’s web site. For patients in the HYCR group, 1-3 of the audio PDF’s will be “assigned” (based on their ITP) for viewing before their next CR visit, with content discussed with the appropriate CR staff person during their next remote or center-based visit.

The following table (Table 3) provides a descriptive summary of the CR protocol for subjects in the two study groups of iATTEND.

Table 3. Summary of the CR protocol for subjects in the two study groups of iATTEND.

	Hybrid CR	Center-Based CR
Staff : Subject ratio (contact time, setting)	1:1 (12 to 15 min, individual setting)	4:1 (60 min, group setting)

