Programming for CR session	
 • 2 to 3 sessions each week • At least 1 and no more than 12 of the sessions will be center-based • Remainder of 36 sessions will be remote-/home-based with TM 	All sessions will be center-based sessions, 2 to 3 sessions each week
Recommended total number of sessions	36	36
Exercise intensity range (85)	60%-80% of heart rate reserve or RPE 11-14	60%-80% of heart rate reserve or RPE 11-14
Recommendation for purposeful exercise outside of formal CR	Encouraged, ad libitum	Encouraged, ad libitum
Patient monitoring	ECG telemetry and resting and exercise blood pressure monitoring for 1-6 center-based visits, with HR monitors provided for all home/remote telemedicine visits.	ECG telemetry and resting and exercise blood pressure monitoring for 3-6 center-based visits. Additional monitoring based on clinical indications
Patient education	28, 7-15 min audio PDFs	8, 45-60 min group lectures
Completion of individual treatment plan	At baseline; 30, 60 and 90 days; at discharge	At baseline; 30, 60 and 90 days; at discharge
Outcomes routinely assessed before and after CR, and used for iATTEND	
 • Nutrition: Rate Your Plate • QOL: Dartmouth COOP • Functional Capacity: MET level* • Depression: PHQ-9 	
 • Nutrition: Rate Your Plate • QOL: Dartmouth COOP • Functional Capacity: MET level* • Depression: PHQ-9
RPE = ratings of perceived exertion; COOP = cooperative functional assessment; TM=telemedicine		
*Change in MET (metabolic equivalent of task) level during training from week 1 to final week of CR		

4.4. Program Operations.

One concern with any home-based CR program that periodically incorporates some form of synchronized communications might be that “the use of staffing resources per patient encounter is less efficient”. To minimize potential inefficiencies in iATTEND, a schedule for HYCR at Henry Ford Main Campus will be adopted that allocates up to 4, one hour blocks of

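### The planned analysis of actionable events around exercise sessions does not allow for different observation of the two arms, so a simple comparison by arm could make hybrid rehabilitation look safer for minor events

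*Combined protocol and SAP*

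**What the plan says.** Section 6.1.2 states: "A secondary analysis is planned of actionable events (both AE and SAE) sustained immediately prior to, during, or immediately after" a training session. It covers major events and also everyday ones, such as ischemia, persistent hypotension or low blood sugar, that lead staff to hold back or stop exercise or to call the physician. It gives no denominator, no comparison method and no rule for sessions that staff do not watch. Section 10 does not mention this analysis, and it is not among the endpoints in Section 5.2.

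Table 3 describes staff contact as "1:1 (12 to 15 min, individual setting") for HYCR and "4:1 (60 min, group setting") for CBCR. Its monitoring row gives HYCR "ECG telemetry and resting and exercise blood pressure monitoring for 1-6 center-based visits". For remote contact, the same row adds to this: "with HR monitors provided for all home/remote telemedicine visits". CBCR has the same ECG and blood pressure monitoring for 3 to 6 visits, with more if clinically indicated.

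On session mix, Table 3 says of HYCR: "At least 1 and no more than 12 of the sessions will be center-based", with the rest delivered remotely by TM. Section 4.3.5.b sets out a different mix for patients without a preference: "they will be scheduled to complete 12 of their 36 visits as HYCR-TM, with the remainder being home-based without TM (up to one time per". The limit on such home sessions is thus a weekly one, and center visits may also make up the balance. Section 4.4 also allows audio-only contact in some cases.

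Section 6.1.1 collects SAEs and selected AEs in both arms through follow-up visit 2. Appendix A describes six-monthly DSMB meetings, "during which a comparison will be made of any excess, untoward events".

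**The concern.** Some of the events in Section 6.1.2 exist in the record only because a staff member saw, measured or acted on something. A CBCR patient is with staff for the whole hour. A remote HYCR patient is in contact for about a quarter of that time, and for a home session without TM no staff contact is described. With equal true rates, fewer such events would then be written down for HYCR.

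Section 3.4 says that a successful trial would be put forward as a model to other health systems and insurers. A table of actionable events by arm, with no statement about ascertainment, would probably be read as comparative safety evidence, and the error would be in the reassuring direction.

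**Working it through.** **The plan's own figures.** Section 6.1.2 has no event rate, sample size or power, so there is nothing to reproduce for it. The attendance inputs borrowed below are sound: with 135 per arm, SD 13 and a difference of 4.5 sessions (Section 10.2), power is 0.81, in line with the stated 80%.

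**Step 1. Observed time over 36 sessions.** Assumption: detection is proportional to staff contact minutes. CBCR: 36 × 60 = 2160 minutes. HYCR: 60 × center sessions + m × TM sessions + 0 × home sessions without TM, with m = 12, 13.5 (midpoint) or 15. HYCR center sessions are credited with the full 60 minutes.

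| HYCR mix | Source | Minutes (m = 12 / 13.5 / 15) | Share of 2160 |
|---|---|---|---|
| 1 center + 35 TM | Table 3 | 480 / 532.5 / 585 | 0.22 / 0.25 / 0.27 |
| 12 center + 12 TM + 12 home | illustrative split under 4.3.5.b | 864 / 882 / 900 | 0.40 / 0.41 / 0.42 |
| 12 center + 24 TM | Table 3 | 1008 / 1044 / 1080 | 0.47 / 0.48 / 0.50 |
| 24 center + 12 TM | 4.3.5.b | 1584 / 1602 / 1620 | 0.73 / 0.74 / 0.75 |

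On this assumption, equal true rates would appear as a per-session rate ratio (HYCR to CBCR) of about 0.22 to 0.74. An extreme mix of 1 center, 12 TM and 23 home sessions would give 0.09 to 0.11. I leave it out of the range because it needs a home session without TM in 23 of about 26 weeks.

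**Step 2. A different proxy: staff-minutes per patient.** If the CBCR ratio means four patients to one staff member (the label appears reversed), a CBCR session gives 60/4 = 15 staff-minutes per patient, or 36 × 15 = 540 over the course.
- 12 center + 24 TM: (12 × 15 + 24 × 13.5)/540 = 504/540 = 0.93.
- 1 center + 35 TM: (15 + 35 × 13.5)/540 = 487.5/540 = 0.90.
- 12 center + 12 TM + 12 home: (12 × 15 + 12 × 13.5)/540 = 342/540 = 0.63.

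The gap nearly closes for TM sessions. It does not close where sessions have no TM.

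**Step 3. Self-report.** If a share c of unobserved events is reported by patients, capture is f + (1 − f) × c, where f is the observed share. For 12 center + 24 TM at 15 minutes (f = 0.50), c = 0.5 gives 0.75 and c = 0.75 gives 0.875. For 1 center + 35 TM at 15 minutes (f = 0.271), the values are 0.635 and 0.818.

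**Step 4. Completed sessions.** Both arms are scheduled for 36. At the detectable difference, HYCR completes 25.5 and CBCR 21, a ratio of 25.5/21 = 1.21. With equal rates and equal capture, raw counts per patient would be 21% higher in HYCR. Combined with Step 1, the count ratio is 0.22 × 1.21 = 0.27 to 0.74 × 1.21 = 0.90. The two distortions run in opposite directions, so counts without a denominator cannot be interpreted.

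**Step 5. What a test would do, if one were run.** The plan contains none, so this is only an illustration. Take 12 center + 24 TM at 15 minutes, equal true rates assumed at 0.25% to 2% per session, and a conditional binomial test at two-sided 0.05. The chance of a falsely significant lower per-session rate in HYCR is 13% to 89% with no self-report, 4% to 30% with half reported, and 2% to 10% with three quarters reported. The nominal value for that tail is 2.5%.

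**The case against.** The strongest reply is that Section 6.1.2 announces no between-arm test, hypothesis or safety claim. That is correct. A reader might infer that the plan contains a biased significance test and that the percentages in Step 5 are properties of this trial. The documents do not support that. What stands is narrower: an arm-level table without a denominator or a note on ascertainment invites the comparison.

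A reader might also infer that the DSMB will be misled. The comparison in Appendix A follows a description of major events such as death and hospitalization, and the same paragraph sends minor events to the subject's file. The natural reading is that the DSMB compares major events, whose capture depends little on staff watching. Section 6.1.1 does forward selected AEs to the DSMB, so the separation is not complete, but the DSMB route is weak support.

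A third tempting reading is that any one ratio from Step 1 measures the bias. It does not: contact minutes are an unproven proxy, one-to-one contact may be more attentive than group supervision, and several of the listed events are felt by the patient and can be reported.

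Monitoring should not be overstated either. The two arms share an upper limit of 6 monitored center visits, so most CBCR sessions also lack routine ECG and exercise blood pressure. HYCR patients have heart rate monitors for TM visits, and those who opt for remote sessions report resting blood pressure before each one. It would also be wrong to say that HYCR has more planned sessions; 4.5 is the detectable difference in completed sessions.

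The manual of operations may hold a capture procedure, but it is not among the documents. None of these points equalizes capture of staff-dependent minor events.

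**Conclusion.** The concern holds in limited form. For minor events that depend on staff observation or action, the plan provides for unequal ascertainment and does not allow for it, so a simple comparison of counts or rates by arm could make HYCR look safer when true rates are equal. Deaths, hospitalizations and emergency visits are largely unaffected.

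The direction for per-session rates is clear and the size is not. The range of 0.22 to 0.74 rests on detection following contact minutes. The ratio is about 0.9 for center-plus-TM schedules if detection follows staff-minutes per patient, and about 0.82 to 0.88 in the two Table 3 schedules worked above if three quarters of unobserved events are self-reported. True event rates and self-report are not in the documents. No endpoint or sample size is affected. Severity is minor.

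**What to change.** In Section 6.1.2, with a matching entry in Section 10:

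- Report actionable events per completed session and per patient, tabulated by session type (center, TM, home without TM).
- Limit any between-arm safety statement to events whose capture does not depend on staff watching: death, hospitalization, emergency visit, and fall needing medical attention. Ask about these in identical terms in both arms at the existing follow-up visits and telephone calls.
- Present staff-observed minor events descriptively, with the difference in ascertainment stated beside the table.
- Reconcile Table 3 and Section 4.3.5.b on the HYCR session mix. They disagree on the number of center sessions and on whether home sessions without TM occur, and sessions cannot be classified until that is settled.

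The cost is some SAP wording, a session-type field in the tabulation and a short common set of questions. The downside is that the comparative safety statement will rest on fewer events.
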